
## **Study Methods**

**Design:** A two-group, pre-test/post-test experimental design will be used to examine the feasibility and estimate the effects of a sleep intervention (SLEEP-Extend) designed to extend sleep duration in obese, young adults with short sleep and IR. Participants will wear actigraphy watches for one week of baseline sleep data and for an additional four weeks during the intervention.

**Sample/Setting:** We will recruit from Emory Hospital and Emory affiliated hospitals (Children's Healthcare of Atlanta, Emory St. Joseph's, Emory Johns Creek, Emory Midtown) through nursing staff email listservs as well as through flyers on Emory University campus and in areas that might attract young adults, through course web announcements, listservs for student emails and through social media, 20 obese individuals age 18-25 years old with short sleep (duration less than 7hrs./night) and evidence of IR [HOMA-IR levels  $\geq 2.1$  using serum sample (Esteghamati et al., 2010)] (See Timeline). We want to ensure 10 participants are in both groups; therefore, based on our previous experience recruiting from this age group, we will recruit individuals to give us a final N=20 (10 in each group).

Inclusion criteria: 1) Age 18-25 years old, 2) Self-report short sleep, 3) BMI  $\geq 30$  (the World Health Organization's classification of being obese, 4) IR determined by serum analysis, 5) Be willing to extend time in bed (See intervention below) by one hour total per night, and 6) Read and speak English.

Exclusion criteria (all self-report): 1) Night shift workers (circadian disruption can alter glucose and insulin levels), 2) Diagnosed sleep disorder (e.g., sleep apnea, restless leg syndrome,) which may impact glucose, insulin, and other hormones, 3) Medical diagnosis of diabetes or pre-diabetes, 4) Pregnant or lactating women or history of gestational diabetes, 5) Actively or intentionally trying to lose or gain weight (alteration of glucose metabolism/insulin secretion), 6) Hospitalization in past 3 months for medical or psychiatric condition, or 7) Major chronic disease (e.g., cancer, Lupus). The 5-week study will be conducted during the middle of the semester when the longer holidays and final exams do not occur.

1. Data samples will not be saved/banked or archived for future use.
2. Community Participation: Our target group consists of young adults ages 18-25 that are not diagnosed with pre-diabetes or diabetes, therefore we are not recruiting from a clinic population. For this pilot and feasibility study will recruit from Emory Hospitals (nursing staff) and Emory University and surrounding areas. Persons in this group will not be involved in the design or conduct of the study outside of participation. Once data analysis is complete, participants will receive their blood sample results as well as their actigraphy results via written form (a letter will be sent to them in the manner they choose---- email or regular mail).

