### **Outcome Measures:**

**BMI and baseline blood samples will be obtained at the screening visit.** All other measures will be assessed at the baseline visit and at the end of the 4-week intervention period except for the following: 1) Actigraphy watch will be worn continuously, and daily sleep diary completed for the entire study period, 2) The sleep hygiene pre/post-test and safety pre/post-test (control group only) will be given prior to intervention, immediately post intervention and at end of 4-week intervention period (3 time points), 3) Participant characteristics questionnaire only at baseline, and 4) Both groups will receive the exit survey at end of 4 week intervention period. **Insulin Resistance:** A) Glucose and insulin levels will be measured from fasting serum samples. B) Insulin Resistance will be calculated from the measured glucose and insulin levels using standard formulas. Briefly, serum samples will be collected via venipuncture and analyzed at Cardiovascular Specialty Laboratories, Inc (Atlanta, GA) using standard laboratory approaches with calibrated equipment (See letters of cooperation, from [name] and [name]). These two values will be used to calculate the homeostatic model assessment of insulin resistance (HOMA-IR; blood glucose level X insulin level, divided by 22.5). Elevated values indicate IR. A cutoff score of HOMA-IR < 2.1 as normal and HOMA-IR  $\geq$  2.1 as elevated (evidence of IR) will be used as determined in non-diabetics (Esteghamati et al., 2010). **Sleep Duration:** Using wrist actigraphy (Motionlogger, AMI, Ardsley, NY) along with a sleep diary (required to help validate and score actigraphy data; Martin & Hakim, 2011), we will objectively monitor each participant's 24-hour sleep-wake cycle to obtain average sleep duration (total sleep time) for one week (baseline) prior to random assignment to group and will continue monitoring during the 4 week intervention period. All participants wear the device (looks like a watch) on the wrist continuously for a total of 5 weeks (1 week for baseline sleep and 4 weeks of intervention period), except while bathing or swimming. Leproult and colleagues (2015) had success with adults wearing a wrist actigraph continuously for a total of 8 weeks. This device contains a light sensor that stores activity counts in 1-minute epochs and will detect the onset and offset of sleep using concurrent data from sleep diaries (Buysse et al., 2008; Morgenthaler et al., 2007). The Motionlogger was successfully validated against polysomnography on dimensions of sleep patterns: sleep onset latency, wake time after sleep onset, total sleep time (sleep duration), and sleep efficiency percentage (Cole et al., 1992). Data for each sleep component will be averaged over the 7 days for each week of the protocol (e.g. average sleep efficiency percentage, average total sleep duration) for analysis. Actigraphy has been compared to polysomnography to detect sleep and wakefulness and found to have a sensitivity of .965 and accuracy of .863 (Marino et al., 2013). The sleep diary is necessary to record data to help interpret actigraphy data (time in bed, time awake, and anything that occurs during the night such as waking up in the middle of the night). Participants in the SLEEP-Extend group will also use a daily sleep diary to record any sleep hygiene practices they use. Participants in the control group will use the same daily sleep diary as the SLEEP-Extend group with the difference of recording any safety practices used rather than recording sleep hygiene practices used. **Sleep Hygiene Knowledge:** To assess

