### **PROCEDURES:**

For interested participants, initial screening on the telephone for age, average sleep duration, and BMI will be done and if eligible, an appointment will be set and instructions for fasting (participant will be instructed to not eat or drink anything for 8 hours) for the screening visit (Visit #1). At Visit #1 we will obtain written informed consent that will include information on screening process: eligibility of IR (from blood sample) and height and weight measures will be obtained for BMI. Blood samples will be analyzed within one week. If HOMA-IR level is elevated in these obese individuals with short sleep, then they will be contacted and 2 additional appointments will be made. If they do not have elevated HOMA-IR levels, the researcher will call and thank them for their interest and let them know they are not eligible. Visit #2, baseline (BL) visit, will be within 2 weeks of obtaining initial blood result and consent will be confirmed (for enrollment in the study) and other BL data will be collected. Also, participants will be given a sleep diary to complete and an actigraphy watch to wear for one week for BL sleep assessment. During visit #3 (intervention visit) which is one week after BL visit, the BL actigraphy data will be downloaded and the participant instructed to continue to wear the watch for 4 more weeks. Randomization to groups will occur, and each group will receive the appropriate intervention content for the group. Immediately after the intervention, the appropriate knowledge post-test will be given according to assigned group. The SLEEP-Extend group will decide on when they are able to extend their TIB. After 2 more weeks both groups will receive a telephone call to reinforce content and answer questions about extending TIB and sleep hygiene for SLEEP-Extend group and safety information in the control group. At this telephone call the final appointment will be set for 2 weeks later and for a reminder to come in fasting. Visit #4 is the at the end of the 4-week intervention period, and data collection will include drawing of blood samples, downloading of actigraphy data with return of the watch and daily sleep diary and completing responses to standard questionnaires. To strengthen the design, we have made time spent with both groups similar throughout the study. All participants will

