4. Visit #1 (screening visit) will include obtaining blood samples to calculate insulin resistance, 2 consecutive nights of pulse oximetry and one week of baseline sleep duration using Actigraphy monitoring. The researcher will meet the subject in a private room located on the university campus and will conduct explanation of consent.
- a. The researcher or GRA will obtain written informed consent and a copy provided to the subject.
  - b. The researcher will confirm the subject has not had anything to eat or drink in the past 10 hours
  - c. A registered nurse (either the researcher or GRA) will obtain the following
    - i. Blood sample will be obtained using standard protocol with universal precautions to obtain fasting serum blood glucose and plasma insulin levels. These levels will be used to calculate insulin resistance. A registered nurse will pierce the subject's skin (usually in a vein located on the inside middle part of the arm) with a very small needle and take the blood into a small tube. This method of taking blood is called a venipuncture. The total amount of blood drawn is about 5 ml or 1 teaspoon. During the blood draw, the subject will feel a pinch that lasts several seconds when the blood sample is taken. The subject may have pain, dizziness, bleeding, or bruising at the site of the blood draw. There is a slight risk of infection and scarring at the site of the blood draw. However, the registered nurse will use proper technique while taking the blood sample in order to reduce unwanted effects.
    - ii. After obtaining the blood sample, the subject will be offered a light snack (granola bar, crackers or cookies) to eat and water or juice to drink.

- iii. Subject blood samples will be labeled using a unique identification number and will be stored in a secure laboratory at Emory University until they can be analyzed by Cardiovascular Specialty Laboratories, Inc. in Atlanta, GA. The blood samples will be destroyed by Cardiovascular Specialty Laboratories, Inc. once analysis of blood levels is completed. IBC protocol submitted and approval is pending.
- d. The researcher or GRA will obtain and instruct in the following:
  - i. Subject height (using a stadiometer) without shoes
  - ii. Subject weight (using a calibrated scale) in light clothing and no shoes
  - iii. Subject body fat analysis (using a hand-held, non-invasive calibrated scale) (Omron Body Logic Pro, Omron Healthcare, Inc., Vernon Hills, IL

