- e. After one week of baseline actigraphy and pulse oximetry monitoring, the subject will return the actigraph and pulse oximeter and data will be downloaded and analyzed for sleep duration and oxygen saturation respectively. The researcher or GRA will access sleep diary information from the SleepBot app by taking a screen-shot of the data and printing it. Sleep diary info on the screen-shot will be deleted and only a paper version of the sleep diary will be retained. If the subject used a paper sleep diary, then it will be returned to the researcher for analysis.
- f. If the subject's average sleep duration is not below 7 hours per night or their insulin resistance level does not meet the inclusion criteria (HOMA-IR is a measure of insulin

resistance and needs to be  $\geq 2.1$  in order to meet inclusion criteria), or if their oxygen desaturation index is  $\geq 5$ /hour they will be thanked for their interest and told they are not eligible for the study. Additionally, if the subject's oxygen desaturation index is  $\geq 5$ /hour, they will be instructed to follow up with a health provider for assessment of possible OSA.

- g. If the subject's average sleep duration is less than 7 hours per night and their HOMA-IR meets inclusion criteria ( $\geq 2.1$ ) and their oxygen desaturation index is  $< 5$ /hour, then the subject will be scheduled for their study enrollment visit (Visit #2) to collect questionnaires/surveys. Subjects will be given \$10 after the screening visit.
5. Visit #2 (Study Enrollment Visit): This visit is done as soon as possible following screening. The researcher or GRA will meet the subject in a private room located on the university campus. The study enrollment visit for all subjects includes randomization to the treatment or control group and completion of:
  - a. Researcher-developed demographic/subject characteristics questionnaire
  - b. Baecke physical activity questionnaire
  - c. Dietary Screener questionnaire
  - d. Meal Timing questionnaire
  - e. Perceived Stress Scale
  - f. Sleep Hygiene Index questionnaire
  - g. Control group only: an investigator-developed safety practices questionnaire
  - h. Each subject will be asked to wear the actigraphy watch continuously for 4 additional weeks and complete daily sleep diary for 4 additional weeks (as previously discussed).
  - i. The intervention will be administered as follows

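### Fasting glucose is measured at screening but counts only inside HOMA-IR, so a person with unrecognised diabetes can be enrolled under a cut-off described as set in non-diabetics

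*Combined protocol and SAP*

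**What the plan says.** In Study Methods, the exclusion list is introduced as "Exclusion criteria (all self-report", and its third item is "Medical diagnosis of diabetes or pre-diabetes". The telephone screen in Informed Consent Process and Visit Details (item 3c) repeats that item. The only laboratory criterion among the inclusions is "IR determined by serum analysis".

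At Visit #1 (Visit Details, item 4c) the nurse is to "obtain fasting serum blood glucose and plasma insulin levels. These levels will be used to calculate insulin resistance". Outcome Measures gives the formula as "HOMA-IR; blood glucose level X insulin level, divided by 22.5" and sets 2.1 as the lower limit of elevated, adding that this cut-off "will be used as determined in non-diabetics".

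Two places turn the result into a decision. PROCEDURES goes forward on an elevated HOMA-IR. Visit Details 4f/4g requires HOMA-IR ≥ 2.1, mean sleep below 7 hours and a desaturation index below 5 per hour. Neither applies glucose in its own right.

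Sleep apnoea is handled differently. A diagnosed sleep disorder is a self-report exclusion, but Visit Details 4d(vi) and 4f add two nights of oximetry and exclude on the result, on the ground that apnoea affects glucose and insulin resistance.

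**The concern.** HOMA-IR is a product, so it cannot tell a high insulin at ordinary glucose from a high glucose at modest insulin. A rule that asks only whether the product reaches 2.1 admits both, and the higher the glucose, the easier it is to pass. The cut-off is described as coming from people without diabetes, yet nothing in screening confirms that condition beyond what the participant has been told by a doctor.

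The trial's stated goal is to delay the onset of type 2 diabetes, and it recruits people selected for obesity, short sleep and insulin resistance. A participant who already has diabetes is outside that goal and outside the population in which the cut-off was set. With ten per arm, one such person carries noticeable weight in the insulin-resistance results.

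**Working it through.** The plan states no figure on this point, so there is none to reproduce.

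**Step 1: how glucose acts in the rule.** Inputs are the formula and the 2.1 cut-off, both from Outcome Measures. Units are not stated there; mmol/L for glucose and µU/mL for insulin are assumed. Rearranged:

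insulin needed = 2.1 × 22.5 / glucose = 47.25 / glucose

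| Glucose | Insulin needed for HOMA-IR 2.1 |
|---|---|
| 5.0 | 47.25 / 5.0 = 9.45 |
| 7.0 | 47.25 / 7.0 = 6.75 |
| 10.0 | 47.25 / 10.0 = 4.73 |

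These glucose values show the slope; they are not offered as diagnostic limits. Doubling glucose from 5.0 to 10.0 halves the insulin needed.

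**Step 2: the rule in the other direction.** Glucose 8.0 with insulin 5.0 gives 8.0 × 5.0 / 22.5 = 1.78, below 2.1. A HOMA-IR under the cut-off therefore does not show that glucose is low.

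**Step 3: chance that at least one such person is enrolled.** N = 20 is from Study Methods. The prevalence p of unrecognised diabetes among those who otherwise qualify is not in the documents, so a range is assumed, with participants treated as independent:

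P(at least one) = 1 − (1 − p)^20

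| Assumed p | Expected number, 20p | P(at least one of 20) |
|---|---|---|
| 0.5% | 0.1 | 9.5% |
| 1% | 0.2 | 18.2% |
| 5% | 1.0 | 64.2% |

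**Step 4: weight of one person.** With 10 per arm:
- Hypothesis H2 (Objectives) compares the proportions with a decrease in insulin resistance. One person is 1/10, or 10 percentage points.
- The Analysis Plan expresses blood levels as percent change. One person's change enters the arm mean at one tenth of its size. As an illustration, an assumed individual change of 50% moves the mean by 50 / 10 = 5 percentage points.

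**The case against.** The strongest reply is that the plan does what it sets out to do. The Community Participation item defines the target as people without a diagnosis of either condition, and a self-reported exclusion implements that. This stands: a reader might infer that passages contradict one another, but they do not. What remains is a gap between a target defined by diagnosis and a cut-off tied to being non-diabetic.

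A reader might also infer that people with diabetes will be enrolled. The documents show only that they can be. The Abstract's figure of 8 million undiagnosed does not settle it: the sentence leaves unclear whether it refers to diabetes or prediabetes, and it is national, not specific to ages 18–25. The chances in Step 3 depend wholly on the assumed prevalence, and a value below 0.5% would give less than the lowest figure shown.

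Nor does the text support saying that the study ignores the glucose result. Glucose enters the eligibility calculation. PROCEDURES and Visit Details item 8 promise a results letter with advice on physician follow-up, and Protection of Human Subjects says abnormal findings will be reported. None of these is an eligibility step, however, and whether they cover people screened out is unclear.

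It would also go too far to say that one such participant decides an arm's result, or that such a person would change more erratically or begin treatment during follow-up. The documents give no basis for either, and Step 4 bounds the effect on H2 at 10 percentage points.

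Finally, this is a 20-person pilot whose first aim is feasibility and acceptability. That limits the seriousness of the gap, but the value needed to close it is already being measured.

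**Conclusion.** The point holds as a gap in eligibility. Diabetes and pre-diabetes are excluded by self-report only, the screening glucose acts only through HOMA-IR, and a higher glucose makes qualifying easier. A person with unrecognised diabetes can therefore be enrolled under a cut-off described as set in non-diabetics. The same route is open to unrecognised pre-diabetes, which exclusion 3 also names.

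The chance of at least one person with unrecognised diabetes among 20 is about 10%, 18% or 64% at an assumed prevalence of 0.5%, 1% or 5%. One person is a tenth of an arm's mean percent change, or 10 percentage points of H2's proportion. These figures rest on the assumed prevalence, on independence and on 10 analysed per arm; the insulin thresholds rest on the assumed units. Closing the gap is a cheap improvement, and the gap does not undermine the pilot's feasibility aim.

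**What to change.** In exclusion 3 (Study Methods) and in Visit Details 4f/4g, apply the Visit #1 fasting glucose as its own eligibility check, against a diabetes standard that the sponsor names, so that the exclusion no longer rests on self-report alone. This mirrors the objective check already added for sleep apnoea. The sponsor should also state whether the check extends to pre-diabetes. PROCEDURES should carry the same rule.

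The cost is an eligibility line, with no extra sample, assay or visit. The downside is a few more screen failures, and more if pre-diabetes is included.

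Separately, reconcile the passages on whether and when people screened out receive their glucose result:
- PROCEDURES, on turning people away as ineligible: "If they do not have elevated HOMA-IR levels, the researcher will call and thank them for their interest and let them know they are not" (last word of the sentence omitted).
- Visit Details 4f: "they will be thanked for their interest and told they are not eligible for the study".
- Community Participation: results are given to participants after the data have been analysed.
- PROCEDURES and Visit Details item 8: a results letter goes to all participants or subjects after the blood is analysed.
- Protection of Human Subjects: abnormal findings are reported to the participant.

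No glucose threshold or referral rule is proposed here; both are for the sponsor to settle.

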### **PROCEDURES:**

For interested participants, initial screening on the telephone for age, average sleep duration, and BMI will be done and if eligible, an appointment will be set and instructions for fasting (participant will be instructed to not eat or drink anything for 8 hours) for the screening visit (Visit #1). At Visit #1 we will obtain written informed consent that will include information on screening process: eligibility of IR (from blood sample) and height and weight measures will be obtained for BMI. Blood samples will be analyzed within one week. If HOMA-IR level is elevated in these obese individuals with short sleep, then they will be contacted and 2 additional appointments will be made. If they do not have elevated HOMA-IR levels, the researcher will call and thank them for their interest and let them know they are not eligible. Visit #2, baseline (BL) visit, will be within 2 weeks of obtaining initial blood result and consent will be confirmed (for enrollment in the study) and other BL data will be collected. Also, participants will be given a sleep diary to complete and an actigraphy watch to wear for one week for BL sleep assessment. During visit #3 (intervention visit) which is one week after BL visit, the BL actigraphy data will be downloaded and the participant instructed to continue to wear the watch for 4 more weeks. Randomization to groups will occur, and each group will receive the appropriate intervention content for the group. Immediately after the intervention, the appropriate knowledge post-test will be given according to assigned group. The SLEEP-Extend group will decide on when they are able to extend their TIB. After 2 more weeks both groups will receive a telephone call to reinforce content and answer questions about extending TIB and sleep hygiene for SLEEP-Extend group and safety information in the control group. At this telephone call the final appointment will be set for 2 weeks later and for a reminder to come in fasting. Visit #4 is the at the end of the 4-week intervention period, and data collection will include drawing of blood samples, downloading of actigraphy data with return of the watch and daily sleep diary and completing responses to standard questionnaires. To strengthen the design, we have made time spent with both groups similar throughout the study. All participants will

receive \$20 after one week of baseline data. At the end of the study, all participants will receive an additional \$30, a certificate of appreciation and a booklet on Healthy Sleep (NHLBI, 2011). Any participants that are noted to have additional risk factors for T2DM will be provided educational material on reducing T2DM risk factors and the suggestion made to follow up with a physician. After serum blood values are analyzed, all participants will be sent a letter with their glucose, insulin and HOMA-IR information along with a description of these values and recommendation for physician follow up. The principal investigator is a registered nurse who will collect the data and administer the sleep intervention. Standard universal precautions will be used during blood draws. Additionally, a GRA, also a registered nurse, will assist with data collection.

**Sample size:** A target sample size of 10 in the SLEEP-Extend group and 10 in the control will be used for this feasibility study (accounting for 20% attrition) given the need for a serum blood test as part of screening a number of participants to meet strict eligibility criteria. Participants will be randomly assigned to either the control or SLEEP-Extend group using a table of random numbers.

**Overview of the SLEEP-Extend Intervention:** The SLEEP-Extend intervention is comprised of two components that will be administered one week after baseline data are collected. The first component consists of aiming to increase sleep duration by increasing time in bed (TIB) by one hour total per night for 4 weeks. Increasing TIB has been a successful strategy used to extend sleep duration in multiple studies (Dewald-Kaufmann, Oort, & Meijer, 2013; Gumenyuk et al., 2011; Kamdar, et al., 2004; Leproult et al., 2015). We will determine with participants when TIB can be extended for one hour total per night (either going to bed earlier or staying in bed later) depending on their preference and instructing participants to increase TIB for one hour total each night for 4 weeks. The second component of the intervention consists of one educational session regarding using sleep hygiene strategies (routine for going to sleep). Healthy sleep hygiene includes strategies such as having a regular bedtime and wake time and avoidance of stimulating food/drink or activities before bedtime (AASM, *Healthy Sleep Habits*; NSF, *Sleep Hygiene*). Participants will use a daily sleep diary to record any sleep hygiene practices they use. The control group will only receive one educational session consisting of safety practices used for an urban environment. Control group participants will use a similar daily sleep diary to record any safety practices they use.

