## **Abstract**

Nearly 30 million Americans have type 2 diabetes (T2DM), a disorder with serious health consequences such as cardiovascular and renal disease. Almost 90 million more have prediabetes, with estimates of 8 million undiagnosed (CDC, National Diabetes Statistics Report). Insulin resistance (IR) is a precursor to prediabetes and T2DM (NIDDK, Insulin resistance and prediabetes). There is evidence of IR in those with short sleep [normal weight (Matthews et al., 2012); obese (Liu, Kushida, & Reaven, 2013)]. The risk for developing diabetes in persons with difficulty in maintaining sleep is 1.84 times the risk of diabetes in those who do not have sleep issues which is very similar to the relative risk detected from another commonly recognized risk factor-- family history of diabetes (1.7-2.3) (Reutrakul & Van Cauter, 2014). For this pilot study we will recruit 20 young adults, accounting for attrition, age 18-25 years who have elevated HOMA-IR (based on established cut points), short sleep duration (< 7 hrs./night) and obesity (BMI  $\geq$  30) (another risk factor for IR), and use a two-group, pre-test/post-test experimental design including objective actigraphy data for sleep. The specific aims are to: 1) evaluate the feasibility and acceptability of a tailored intervention to extend sleep duration (SLEEP-Extend), 2) determine changes in sleep duration after SLEEP-Extend intervention, 3) evaluate IR levels before and after SLEEP-Extend, and 4) explore the potential mediators of diet and physical activity between sleep duration and IR. Screening data will include measures of sleep duration, age, IR and BMI. After enrollment, baseline data will include pre-test of sleep hygiene knowledge, self-report measures of diet and physical activity as well as one week of objective monitoring of sleep using actigraphy. After all baseline data are collected, participants will be randomly assigned to group. The SLEEP-Extend intervention group will receive sleep hygiene education and instructions to increase time in bed by one hour total each night for an additional 4 weeks. The attention control group will receive education on safety practices in an urban environment. Both groups will receive the sleep hygiene post-test immediately after the intervention, and they will continue with actigraphy monitoring for 4 weeks. After the 4-week intervention period, both groups will have measures of IR, BMI, final post-test of sleep hygiene knowledge, self-reported diet and physical activity, and an exit interview, and actigraphy data will be downloaded. This study will examine whether an intervention to extend sleep will result in behavior change to increase sleep duration and improve IR.

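### The number 20 serves as both the intake and the final sample size, which 20% attrition does not allow, and the allocation method as described does not secure 10 per group

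*Combined protocol and SAP*

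**What the plan says.** Three places give the size of the study.

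- Abstract: "For this pilot study we will recruit 20 young adults, accounting for attrition". Here 20 is the intake.
- Study Methods, Sample/Setting: those to be recruited are "20 obese individuals age 18-25 years old with short sleep" and evidence of insulin resistance. The same paragraph then says "we will recruit individuals to give us a final N=20 (10 in each group". Here 20 is first the intake and then the final number.
- Sample size paragraph (under Procedures): "10 in the SLEEP-Extend group and 10 in the control will be used for this feasibility study (accounting for 20% attrition". This is the only place that gives an attrition rate.

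On allocation, Sample/Setting states the aim: "We want to ensure 10 participants are in both groups". The Sample size paragraph states the method: "Participants will be randomly assigned to either the control or SLEEP-Extend group using a table of random numbers". No blocks, fixed arm totals or pre-built list are described, nor who holds the table or how the next entry is hidden. The same part of the protocol has the principal investigator collecting data and delivering the intervention. The Informed Consent Process section has the principal investigator screening callers by telephone.

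**The concern.** One number cannot be both the count before a 20% loss and the count after it. Whoever sets recruitment, budget or approved accrual from this text cannot tell whether to plan for 20 participants or for about 25. Whoever reads it for precision cannot tell whether to expect 10 or 8 completers per group. This matters because the pilot is meant to estimate effects and to support a larger study, and both of its hypotheses compare the groups.

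The allocation question is separate. Equal groups are an aim of the plan, but drawing assignments from a random-number table does not produce them unless a restriction is added. Where the person who screens also treats and measures, the plan should also say how the next assignment is kept unknown until it is used.

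**Working it through.** **Inputs.** Intake 20 (Abstract; Sample/Setting). Final number 20, 10 per group (Sample/Setting). Attrition 20% (Sample size paragraph). Allocation by a table of random numbers (Sample size paragraph). The plan gives no alpha, power, SD or effect size, so there is no power calculation to reproduce. I assume that the 20% applies after randomisation, since the plan does not say.

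**1. Can a final 20 be reproduced?**
- Forward: 20 × (1 − 0.20) = 16 completers, or 8 per group if split evenly. The stated final number is 20, so the gap is 4.
- Backward: 20 / (1 − 0.20) = 25 randomised. Per arm, 10 / 0.8 = 12.5, rounded up to 13, which makes 26 for equal arms.
- The cruder inflation, 20 × 1.20 = 24, does not give 20 either.
- The figure 20 is reproduced only as the number randomised to obtain 16: 16 / 0.8 = 20.

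**2. What the difference means for precision.** The 95% confidence interval half-width for a difference in means, in SD units with n per arm, is t(0.975, 2n − 2) × √(2/n).
- n = 10: 2.101 × √0.2 = 0.94 SD.
- n = 8: 2.145 × √0.25 = 1.07 SD.
- Ratio: 1.07 / 0.94 = 1.14, so the interval is about 14% wider.

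**3. Balance, if the table is used for simple 1:1 randomisation of 20.**
- P(10/10) = C(20,10) / 2^20 = 184,756 / 1,048,576 = 17.6%.
- P(13:7 or more uneven) = 2 × Σ C(20,k) for k = 0 to 7, divided by 2^20 = 275,960 / 1,048,576 = 26.3%.
- P(14:6 or more uneven) = 2 × Σ C(20,k) for k = 0 to 6, divided by 2^20 = 120,920 / 1,048,576 = 11.5%.

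**4. What imbalance costs.** The standard error relative to 10/10 is √[(1/a + 1/b) / (1/10 + 1/10)].
- 13:7: √(0.2198 / 0.2) = 1.05.
- 14:6: √(0.2381 / 0.2) = 1.09.
- Since 14:6 or worse has probability 11.5%, the other 88.5% of simple randomisations cost at most about 5% in standard error.

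These balance figures are at allocation. Dropout can unbalance the final groups further.

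**The case against.** A reader might infer that the study will certainly fall short at 16. The documents do not establish that. Sample/Setting speaks of recruiting so as to reach a final 20, and the Sample size paragraph can be read as 10 per group net of attrition. On that reading nothing is lost; the gross intake is simply missing. This stands, and it is why the defect is an unreconciled number rather than a proven shortfall. It does not remove the defect, because the reading conflicts with the Abstract and the 25 or 26 that it requires is never stated.

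A reader might also take 17.6% as a property of the plan. It is not: a table of random numbers can generate permuted blocks or a fixed 10/10 list, and simple randomisation is inferred from silence. Exact equality is also a poor measure of harm, as the 5% figure at 13:7 shows.

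Nor do the documents say that the table will be open to those enrolling. They are silent. Randomisation follows consent and laboratory confirmation of insulin resistance in both descriptions of the visits, which limits the scope for influencing who enters without removing it. That the principal investigator treats and measures is mainly a blinding matter and does not show failed concealment.

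Finally, this is a feasibility pilot that promises no power or interval width. No stated precision is therefore broken, and a 14% wider interval does not undermine the study.

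**Conclusion.** The point holds as an inconsistency that should be fixed. The plan uses 20 before and after a 20% loss. It must mean either 20 randomised with about 16 completers, or a final 20 with 25 to 26 randomised. The text does not settle which. If it is the first, the half-width for a mean difference is about 1.07 SD rather than 0.94 SD, assuming an even split and the plan's own attrition rate.

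The allocation point holds in a limited form: the stated method does not by itself deliver the balance that the plan wants, and no concealment is described. The 17.6% and 26.3% depend on simple randomisation of 20. The typical loss of precision from imbalance is small, so the stronger reason to act is that restriction and concealment are cheap and cannot be added for participants already allocated.

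**What to change.** **Numbers.** Use one consistent pair in the Abstract, Sample/Setting and the Sample size paragraph.
- Without enrolling more: 20 randomised, about 16 completers (8 per group) expected at 20% attrition, with a 95% half-width of about 1.07 SD for a mean difference.
- If a final 20 is intended: state that 25 will be randomised, or 26 for equal arms.

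Say in either case at which step the 20% loss is counted.

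**Allocation.** Use the random-number table to build a 1:1 permuted-block list with varying block sizes, or a fixed 10/10 list if 20 is the number randomised. Have it prepared by someone who does not enrol participants. Keep it concealed until allocation, for example in sequentially numbered opaque sealed envelopes.

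**Cost.** A few sentences and an envelope set. Under the first option the stated completer number becomes less favourable; under the second, 5 or 6 more participants must be found through a screening process that needs a blood test. Small blocks are slightly predictable to someone who knows past assignments, which varying the block size reduces. A fixed 10/10 list becomes predictable towards its end.
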